6.2.1.3 Data Analysis of Primary Safety and Effectiveness Endpoints

The following analysis populations are defined for the study:

Intent-to-Treat (ITT): [REDACTED]

Per Protocol (PP): [REDACTED]

The primary analysis population for the Primary Safety Endpoint will be the ITT population. The Primary Effectiveness Endpoint will be evaluated in both the ITT and PP populations.

All primary safety and effectiveness endpoints will be tested against the pre-specified performance goals at 6 months with exact, binomial tests.

Clinical Investigation Plan

[REDACTED]

[REDACTED]

[REDACTED]

6.2.1.4 Adaptive Sample Size Re-estimation

[REDACTED]

[REDACTED]

[REDACTED]

[REDACTED]

[figure not shown]
[REDACTED]

[REDACTED]

Clinical Investigation Plan

6.2.1.6 Missing Data

All attempts will be made to ensure subject retention in the study to minimize the amount of missing data. Reasons for withdrawals will be documented and assessed relative to possible relationships to study primary endpoints.

Clinical Investigation Plan

6.2.1.7 Subgroup Analyses

6.2.1.8 Conditional Probability of Meeting 1-Year Primary Endpoints

Clinical Investigation Plan

6.2.2 Secondary Endpoint

The secondary endpoint includes evaluation of a CAEP exercise protocol.

Secondary CAEP Endpoint

H_0 : Mean Slope is Not Equivalent to 100%

$$| \text{Slope} - 100\% | \geq \delta$$

H_1 : Mean Slope is Equivalent to 100%

$$| \text{Slope} - 100\% | < \delta$$

Where, δ = equivalence margin, equal to 35%

CAEP exercise protocol

All capable subjects will be asked to perform a maximal effort CAEP exercise protocol to demonstrate an appropriate and proportional response of sensor-indicated rate in graded exercise tests.

Data from subjects unable to complete at least stage 3 of the exercise protocol (3.6 METS) will be excluded from the analysis, although their results will still be reported. Thirty subjects will provide data contributing to the analysis.

The analysis of these exercise test data will provide an estimate of the slope of the normalized increase in sensor-indicated rate versus normalized CAEP workload for each subject. An analysis of these data will also estimate the 95% confidence interval for the mean slope across subjects, which has a pre-specified success criterion requiring that this confidence interval must fall between slopes of 65% and 135%.

Clinical Investigation Plan

For each subject (i), a slope will be estimated using data points (Y_{ij}) on X_{ij} , where j = individual paired values for subject (i). The estimate of the slope for data from subject (i) is given by:

$$Slope_i = \sum (X_{ij}) (Y_{ij}) / \sum (X_{ij})^2$$

Where, the summations are across individual paired values (j) for subject (i) taken at the end of every completed CAEP stage. The mean slope (SlopeMean) is estimated by the average slope across N subjects:

$$SlopeMean = \sum Slope_i / N$$

Where the summation is over $i = 1, \dots, N$, with N equal to the number of subjects.

The standard error of the mean slope is estimated in the usual manner:

$$SE(SlopeMean) = \left[\sum (Slope_i - SlopeMean)^2 / N(N-1) \right]^{1/2}$$

The test statistic for evaluation of the CAEP endpoint becomes:

Test Statistic = $| / SlopeMean - 100\% | - 35\% | / SE$

Clinical Investigation Plan

(SlopeMean)

The boundary of the critical zone for the above test statistic is equal to $[-t_{0.025, N-1}]$, associated with a one-sided Student's t-test, an alpha value equal to 0.025, and $(N-1)$ degrees of freedom.

The CAEP test will be performed any time after the beginning of the 3-month visit window [REDACTED]

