Schedule of Assessments (continued)	
6-week Visit
 
• Nanostim™ LP assessment and programming• Assess for changes in medications or change in therapy• Assess for AEs 
3-month Visit
 
• Nanostim™ LP assessment and programming• Assess for changes in medications or change in therapy• Assess for AEs• 24-hour Holter monitor with diary (30 subjects)• Graded exercise test (CAEP protocol) until 30 subjects provide data contributing to the analysis) 
6-month Visit
 
• Nanostim™ LP assessment and programming• Assess for changes in medications or change in therapy• Assess for AEs 
Every 6-month Visits
 
• Nanostim™ LP assessment and programming• Assess for changes in medications or change in therapy• Assess for AEs
--	---

Clinical Investigation Plan

Table 1: Schedule of Assessments

Activity	Pre-procedure Assessments		Procedure Assessment	Post-procedure Assessments							Additional Visits
	Screen & Enroll	Baseline		Implant	Post-procedure Assessment	2-week Follow-up Visit ¹	6-week Follow-up Visit ¹	3-month Follow-up Visit ²	6-month Follow-up Visit ²	Every 6-months until study completion ³	
Inclusion Exclusion	✓										
Informed Consent	✓										
Pregnancy Assessment/Test	✓										
Medical History		✓									
Baseline Assessment		✓									
Procedure			✓								
Post-procedure Pre-discharge					✓						
Nanostim™ LP Assessment and Programming				✓	✓	✓	✓	✓	✓	✓	✓
12-lead ECG			✓		✓						
X-ray of a pacemaker					✓						
Follow-up Visit						✓	✓	✓	✓	✓	
24-hour Holter monitor with diary⁴								✓			
Graded exercise test CAEP Protocol⁵								✓			
EQ-5D patient survey					✓	✓	✓	✓			
Additional CRFs (when applicable)											
Adverse Event			✓		✓	✓	✓	✓	✓	✓	✓
Deviation		✓	✓		✓	✓	✓	✓	✓	✓	
Study Withdrawal					✓	✓	✓	✓	✓	✓	
Product Out of Service			✓		✓	✓	✓	✓	✓	✓	
System Revision					✓	✓	✓	✓	✓	✓	
Death			✓		✓	✓	✓	✓	✓	✓	
Healthcare Utilization					✓	✓	✓	✓	✓	✓	

1 ±7 days

2 ±30 days

3 ±45 days

4 All capable subjects are asked to wear a 24-hour Holter and complete a diary, until 30 subjects provide data contributing to the analysis. The preferred window to perform the 24 hour Holter test is between the 3-month and 6-month visit.

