5 All capable subjects are asked to perform a CAEP treadmill test until 30 subjects provide data contributing to the analysis. The preferred window to perform the CAEP treadmill test is between the 3-month and 6-month visit.

Clinical Investigation Plan

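### Does leaving subjects who stop before stage 3 out of the CAEP slope analysis call for a planned confidence interval that includes them?

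*Combined protocol and SAP*

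**What the plan says.** Section 6.2.2 starts from a broad group: "All capable subjects will be asked to perform a maximal effort CAEP exercise protocol". For each subject a line through the origin is fitted to paired values "taken at the end of every completed CAEP stage", giving the "slope of the normalized increase in sensor-indicated rate versus normalized CAEP workload for each subject". The subject slopes are averaged without weights, and success requires that "this confidence interval must fall between slopes of 65% and 135" per cent.

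The analysis set is narrower. Data from anyone who does not "complete at least stage 3 of the exercise protocol (3.6 METS) will be excluded from the analysis, although their results will still be reported". The size is fixed by the number who contribute, not by the number tested: "Thirty subjects will provide data contributing to the analysis". The synopsis repeats this ("Graded exercise test (CAEP protocol) until 30 subjects provide data contributing to the analysis"), as do footnote 5 of Table 1 ("All capable subjects are asked to perform a CAEP treadmill test until 30 subjects provide data contributing to the analysis") and Section 6.4.5.4.

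The visible text does not say in what form the excluded results will be reported, and it plans no mean slope or interval that includes them. The end of Section 6.2.2 is redacted, so a supportive analysis may exist there.

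**The concern.** Entry to the pass/fail set depends on performance in the same test that supplies the endpoint. A subject whose pacing rate does not rise with effort may tire sooner, stop before 3.6 METs, drop out of the mean and be replaced by someone who got further. The 30 analysed would then be a favourable selection, and the interval would describe them rather than all capable subjects who tried the test. This is the only visible hypothesis test of rate response, so a reader would want to know whether the conclusion survives inclusion of the early stoppers. The natural request is a planned all-tested interval, with the conclusion restricted if that interval leaves 65% to 135%.

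**Working it through.** **The plan's own figures.** The limits are 100% ± 35%, that is 65% and 135%. With N = 30, t(0.975, 29) = 2.045 and the interval is mean ± 2.045 × SD/√30. At a mean of 100% it stays inside the limits for any SD up to 35 × √30 / 2.045 = 93.7%. The visible text gives no SD, no expected number of non-completers and no slopes for them, so everything below is assumed.

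**How large could the selection effect be?** Suppose there are two kinds of responder, with mean slopes lo and hi and an SD of 15 within each kind, and an all-tested mean of 65%, where an upward shift matters most. The low share is p = (hi − 65)/(hi − lo). If low responders complete stage 3 with probability c and high responders with probability 0.9, the low share among completers is q = pc / (pc + 0.9(1 − p)). For lo/hi = 30/90 and c = 0.5:

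- p = 25/60 = 0.417
- q = 0.208 / (0.208 + 0.525) = 0.284
- completer mean = 0.284 × 30 + 0.716 × 90 = 73.0%
- expected number tested = 30 / 0.733 = 40.9

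Simulated pass rates for the completer interval (100,000 trials per case):

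| Completion, low v high | 60/70 | 55/75 | 30/90 |
|---|---|---|---|
| 90% v 90% | 2.4-2.9% over the three mixtures | | |
| 70% v 90% | 4.0% | 5.7% | 9.7% |
| 50% v 90% | 7.0% | 13.7% | 29.2% |

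The 29% needs a split into very poor and very good responders, a large gap in completion and a true mean exactly at the limit. The overall completer SD in that case is √(15² + 60² × 0.284 × 0.716) ≈ 31, not 15. With the same mixture and completion rates, the pass rate falls to 9.8% at a true mean of 60% and 1.8% at 55%.

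**How many excluded subjects would overturn a pass?** Take completers with mean 90% and SD 30%: 90 ± 2.045 × 30/√30 gives 78.8% to 101.2%. Add k excluded subjects with the same SD.

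- Mean slope 25%, k = 7: pooled mean (30 × 90 + 7 × 25)/37 = 77.7%, lower limit 64.6%. Six are not enough.
- Mean slope 50%, k = 18: pooled mean (2,700 + 900)/48 = 75.0%, lower limit 64.7%.

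Over completer means of 85-100% and SDs of 20-40%, the number needed is 3 to 13 at an excluded mean of 25% and 7 to 36 at 50%. If early stoppers respond like completers, the mean does not move.

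**Would an all-tested interval tell the two explanations apart?** Suppose stopping reflects fitness alone, 60% complete, and the true slope is 80%. If early stoppers' slopes are unbiased, the all-tested interval passes in about 95-100% of simulated trials. But Section 14.2.1 says the device senses right-ventricular blood temperature, and someone who stops before stage 3 contributes at most stages 0 to 2, which is 6 minutes and 2.8 METs (Appendix A). If the response is still building then, a truncated slope is too low even when the device works. With early stoppers' slopes reduced by 20%, 30% or 40%:

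| Reduction | All-tested mean | All-tested interval passes |
|---|---|---|
| 20% | 0.6 × 80 + 0.4 × 64 = 73.6% | about 91-93% |
| 30% | 0.6 × 80 + 0.4 × 56 = 70.4% | about 47-49% |
| 40% | 0.6 × 80 + 0.4 × 48 = 67.2% | about 10-11% |

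The completer interval passes in over 99% of the same trials. The all-tested pass rates also depend on how noisy the short tests are, and more noise lowers the first two. An all-tested failure could therefore mean a poor device or only short tests.

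**The case for a change.** The strongest argument for a change is that saying results will be reported does not fix which summary is shown or how it bears on the conclusion. The extra interval would cost almost nothing: values are taken at each completed stage and a Graded Exercise Test Form is already submitted. Section 6.2.2 gives no reason for the stage-3 cut-off, and a subject who stops after stage 2 has three points (stages 0, 1 and 2), so a slope can be computed.

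Much of this stands. The selection effect is possible, the form of reporting is open, and a descriptive all-tested mean would do no harm. What does not follow is that the plan is wrong without it. The cut-off and the refill to 30 are fixed in advance, so neither can be tuned to the data. Inclusion criterion 1 admits some subjects because of low physical activity, so an ordinary non-device reason for stopping early is built into the population. A rule tying the conclusion to the all-tested interval would replace one possible bias with another whose direction is easier to foresee. Without such a rule, what is left is a display of results that the plan already undertakes to report.

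**Conclusion.** No change to the plan. The stage-3 rule is a fair trade-off: it gives up coverage of early stoppers to obtain slopes over a wider range of workload. The unspecified form of reporting is a gap that analysts will fill sensibly, by showing the number tested, the number excluded, the reasons for stopping and the individual slopes. The formal test is sound for the group it covers, and its result should be stated as applying to subjects able to complete stage 3.

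A selection effect is possible but not shown. At the 65% limit it might raise the pass rate from 2.4-2.9% to anywhere between 4% and 29%, under mixtures and completion rates that no document figure supports, and it falls to 2-10% for true means of 55-60% in the most extreme mixture. The primary safety and effectiveness endpoints are untouched. The judgement rests on the visible text; a supportive analysis in the redacted end of Section 6.2.2 would only strengthen it.

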6.2.3 Supplementary Endpoints

The following supplementary endpoints will be evaluated at 12 months after implant.

6.2.3.1 Supplementary Safety Endpoint Evaluation at 12 Months

$H_0: \text{CFR} \leq 84.5\%$ vs. $H_1: \text{CFR} > 84.5\%$

A sample size of 600 evaluable subjects [REDACTED] establishing a two-sided 95% confidence interval for CFR, with a lower bound exceeding 84.5%, based on an exact binomial distribution.

Subjects who leave the study before their 1 year visit will be censored at the time they leave the study. Therefore, any complications occurring in subjects who depart the study prior to their 1 year visit will be included in this analysis.

Based on the above assumptions, the total enrollment is expected to be 667 subjects, [REDACTED]

Successful demonstration of an 86 % CFR at six months does not preclude 84.5 % CFR at one year.

6.2.3.2 Supplementary Effectiveness Endpoint Evaluation at 12 Months

$H_0: \text{Rate} \leq 85.0\%$ vs. $H_1: \text{Rate} > 85.0\%$

A sample size of 600 subjects [REDACTED] establishing a two-sided 95% confidence interval for successful sensing and pacing, with a lower bound exceeding 85.0%, based on an exact binomial distribution.

The inability to sense or pace within the programmable range available in the Nanostim device, resulting in device repositioning, replacement, or removal will also be captured in the associated safety endpoints.

Clinical Investigation Plan

6.2.3.3 Data Analysis of Supplementary Safety and Effectiveness Endpoints

The supplementary safety and effectiveness endpoints must be met at the 1-year evaluations, [REDACTED]

All

supplementary safety and effectiveness endpoints will be tested against the pre-specified performance goals at 12 months with exact binomial tests.

6.2.4 Additional data

The following additional data will be recorded and reported:

- All adverse events, and whether or not each is device-related or procedure-related
- Implant success rate and reasons for unsuccessful implant
- Device handling characteristics at implant
- Number of device repositioning at time of implantation
- Implant duration, fluoro duration, and time from implant to hospital discharge
- Final LP placement
- Demographics: gender, age, ethnicity, race, indication for pacemaker implant
- Medical history
- Use of beta blocker, ACE, ARB, anti-coagulation, anti-arrhythmic, and anti-platelet medications
- A table and histogram across all subjects of remaining longevity at the six-month and 1-year visits, as displayed by the programmer based on delivered therapy, programmed settings, percent pacing, and measured pacing impedance. Average pacing rate, impedance, pulse amplitude, pulse duration and percentage pacing will also be reported for all visits.
- Hospitalizations
- Mortality

Holters

All capable subjects will be asked to wear a 24-hour Holter monitor and complete a diary, until 30 subjects provide data contributing to the analysis. [REDACTED]

[REDACTED]

[REDACTED]

[REDACTED]

[REDACTED]

[REDACTED]

[REDACTED]

Clinical Investigation Plan

[REDACTED]

[REDACTED]

[REDACTED]

[REDACTED]

[REDACTED]

[REDACTED]

6.2.5 Definitions used in LEADLESS II study

Adverse Event: Any unfavorable clinical event which impacts, or has the potential to impact the health or safety of a subject caused by or associated with a study device or intervention.

Complication: A device- or procedure-related serious adverse event, including any adverse event that prevents initial implantation.

Cardiac Tamponade: Confirmed or suspected accumulation of fluid in the pericardial space.

Cardiac Perforation: An excursion of the Nanostim™ LP through the cardiac muscle. Signs and symptoms of a perforation by Nanostim™ LP may include radiographic evidence of excursion of the LP into the pericardial sac, abnormal echocardiography indicative of a perforation, the accumulation of fluid in the pericardium, cardiac tamponade, or subject symptoms such as chest pain and discomfort.

Device-malfunction: the failure of a device to meet its performance specifications or otherwise perform as intended. Performance specifications include all claims made in the labeling for the device. The intended performance of a device refers to the intended use for which the device is labeled or marketed.

Clinical Investigation Plan

Diaphragmatic/Phrenic Nerve Stimulation: Electrical activation of the diaphragm muscle by the device output pulse. The abrupt diaphragmatic contraction is noted clinically as hiccups associated with each pacing stimulus. The pacing stimulus may stimulate the diaphragm either directly or indirectly via the phrenic nerve.

Dislodgement: The movement of the Nanostim™ LP from its originally implanted position resulting in elevated pacing thresholds or a decrease in sensing.

Elevated Pacing Thresholds: Pacing thresholds > 2.5 V at 0.4 ms at implant. Following lead maturation at 6-8 weeks, an increase in pacing thresholds of 1.2 V at 0.4 ms or greater between visits. This definition is intended to serve as a guideline and it is understood that individual subjects may have unique situations.

Implant procedure duration: Defined as the time from delivery catheter and Nanostim™ LP insertion to removal.

Implant success rate: Defined as the number of subjects leaving the implant procedure with an implanted and functioning Nanostim™ LP device, divided by the number of subjects in whom implantation is attempted.

Loss of Capture: The inability of the device's output pulse to result in depolarization and contraction of the ventricle. Causes include insufficient stimulus strength, separation of the electrode from the myocardium and placement of the stimulating electrode in contact with a non-responsive portion of the myocardium such as scar tissue. Delivery of an output pulse at a time when the myocardium is physiologically refractory is not loss of capture, since capture is not physiologically feasible.

Loss of Sensing: A condition in which the pulse generator is unable to sense intrinsic cardiac signals.

Oversensing: The detection of inappropriate electrical signals by the pulse generator's sense amplifier. These signals, such as myopotentials, electromagnetic interference, or T waves must be of sufficient duration to interfere with normal device function.

Procedure duration: Defined as the time from 18F femoral introducer insertion to removal.

Serious Adverse Event (SAE): Any untoward medical occurrence that:

- a. Led to death,
- b. Led to serious deterioration in the health of the subject, that either resulted in
 1. A life-threatening illness or injury, or
 2. A permanent impairment of a body structure or a body function, or
 3. In-patient or prolonged hospitalization, or

Clinical Investigation Plan

4. Medical or surgical intervention to prevent life-threatening illness or injury or permanent impairment to a body structure or a body function, or requires an invasive strategy to remedy, or
 - c. Led to fetal distress, fetal death or a congenital abnormality or birth defect.

NOTE: Planned hospitalization for a pre-existing condition, or a procedure required by the CIP, without serious deterioration in health, is not considered a serious adverse event.

Sponsor understands that the following items meet the definition of serious adverse event if they require hospitalization or prolong hospitalization, even though an invasive approach may not be necessary to resolve: AV fistula, pseudoaneurysm, blood transfusions, tricuspid valve damage, pericardial effusion, pulmonary embolus, device dislodgement, right ventricular perforation, thrombus formation on the device, ventricular arrhythmias even if not associated with an invasive strategy to remedy.

Non-invasive means such as device re-programming do not meet the criteria for medical or surgical intervention.

Time to discharge: Defined as the time from introducer sheath removal to discharge.

Unanticipated adverse device effect (UADE): Any serious adverse effect on health or safety or any life-threatening problem or death caused by, or associated with, a device, if that effect, problem, or death was not previously identified in nature, severity, or degree of incidence in the investigational plan or application (including a supplementary plan or application), or any other unanticipated serious problem associated with a device that relates to the rights, safety, or welfare of subjects. [21 CFR 812.3(s)]

Unavoidable adverse event: An unavoidable AE is defined as an adverse event related to the implant procedure that is expected to occur for a projected duration in all subjects.

Undersensing: The failure of the pulse generator to sense R-waves, causing delivery of inappropriately timed, asynchronous or competitive output pulses. Undersensing can sometimes be corrected by programming the device to a more sensitive setting, i.e., decreasing the millivolt value.

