6.3.2 Exclusion Criteria

Subjects will be excluded if they meet **any** of the following.

1. Subject has known pacemaker syndrome, has retrograde VA conduction, or suffers a drop in arterial blood pressure with the onset of ventricular pacing; or
2. Subject is allergic or hypersensitive to < 1 mg of dexamethasone sodium phosphate (DSP);
3. Subject has a mechanical tricuspid valve prosthesis; or
4. Subject has a pre-existing endocardial pacing or defibrillation leads; or
5. Subject has current implantation of either conventional or subcutaneous implantable cardioverter defibrillator (ICD) or cardiac resynchronization therapy (CRT) device; or
6. Subject has an implanted vena cava filter; or
7. Subject has evidence of thrombosis in one of the veins used for access during the procedure; or
8. *Subject had recent cardiovascular or peripheral vascular surgery within 30 days of enrollment; or
9. Subject has an implanted leadless cardiac pacemaker

Clinical Investigation Plan

*Recent cardiovascular or peripheral vascular surgery within 30 days of enrollment is defined as the following:

- **Percutaneous valvular correction \leq 30 days**
- **Femoral or abdominal vascular procedure involving incisional access \leq 30 days**
- **Peripheral arterial endovascular procedure or surgery \leq 30 days**
- **Cardiac surgery \leq 72 hrs with ongoing complications, ongoing mediastinal drainage, or re-do sternotomy attributed to bleeding \leq 30 days**
- **Tricuspid valve replacement or annuloplasty \leq 30 days**
- **Any endovascular procedure with specified complication \leq 30 days**
 - **Femoral access site-vascular complication including hematoma requiring transfusion, surgical intervention or prolongation of hospitalization, arterio-venous fistula, pseudoaneurysm or tear**
 - **New pericardial effusion more than trivial/mild, or requiring percutaneous/surgical drainage**
- **Acute deep venous thrombosis**

6.4 . Study Procedures

This section provides a description of all the clinical-investigation-related procedures that subjects undergo during the clinical investigation. **Figure 1** illustrates study flow and **Table 1** lists a summary of scheduled assessments. Refer to **Figure 1** and **Table 1** for an overview of the required study procedures at each interval or study visit.

[figure not shown]

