Low-grade fever (<100 degree Fahrenheit fever or < 37.8 degree Celsius)	< 48 hours
Percutaneous access pain	< 72 hours
Mild to moderate bruising/ecchymosis at percutaneous access site	< 72 hours
Sleep problems (insomnia)	< 72 hours
Back pain related to laying on the table	< 72 hours

If an **UNANTICIPATED ADVERSE DEVICE EFFECT** occurs, Sponsor requires the investigator to report any UADE to the Sponsor as soon as possible [21 CFR 812.150 (a) (1)], but within 3 calendar days [Sponsor's requirement] of the investigator's knowledge of the event, unless local requirements are more stringent, and to the IRB/MECs per IRB/MEC requirements. Sponsor will take any steps necessary to investigate the event, and will be responsible for notifying FDA and all other participating IRBs/MECs and investigators.

Should sponsor determine, either through physician reports or in-house testing, that an unanticipated adverse event presents an unreasonable risk to participating subjects, sponsor will suspend the clinical investigation and notify all participating investigators, IRBs/MECs and FDA.

Sponsor will provide to FDA on a quarterly basis an interim safety and adverse event report.

Clinical Investigation Plan

Table 5: List of foreseeable adverse events and anticipated adverse device effects

*Access site bleeding event	
Air embolism	Induced ventricular ectopy or arrhythmias
Angina pectoris	Infection, local at access site, or systemic
Arterial puncture	Insufficient cardiac output
AV fistula	Intermittent capture
Bladder puncture	Interruption of desired pacemaker function due to electrical interference, either electromyogenic or electromagnetic
Blood transfusion	Keloid formation
Blunted or poor sensor response	Loss of normal device function due to battery failure or component malfunction
Body rejection phenomena	Muscle and nerve stimulation
Bowel penetration	Myocardial damage
Cardiac arrhythmias	Myocardial infarction
Cardiac dissection	Myocardial irritability
Cardiac perforation	Oversensing
Cardiac tamponade	Pacemaker syndrome
Chronic nerve damage	Palpitations
Damage to vessels	Pericardial effusion or rub
Death	Pericarditis
Device dislodgment	Phrenic nerve/diaphragmatic stimulation
Dizziness	Pneumothorax
Dyspnea	Premature battery depletion
Embolism	Programmer/software anomaly
Endocarditis	Pseudoaneurysm formation
Excessive Bleeding	Psoas abscess
Exit block	Reaction to contrast
Failure to capture/loss of capture	Septic arthritis

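### Section 6.2.5 defines cardiac tamponade as any confirmed or suspected pericardial fluid, so tamponade and effusion cannot be told apart reliably in the adverse event counts

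*Combined protocol and SAP*

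**What the plan says.** The definitions in section 6.2.5 include "Cardiac Tamponade: Confirmed or suspected accumulation of fluid in the pericardial space". There is no further condition on amount, circulatory effect, drainage or confirmation. Pericardial effusion has no entry of its own in that section.

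Other places use the two terms as if they were different things:

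- The perforation definition in section 6.2.5 names among its possible signs "the accumulation of fluid in the pericardium, cardiac tamponade, or subject symptoms such as chest pain and discomfort".
- The note under the SAE definition, also in section 6.2.5, lists events that are serious if they require or prolong hospitalization. The list includes "pericardial effusion, pulmonary embolus, device dislodgement, right ventricular perforation". Tamponade is not in it.
- Table 5 in section 9.0 has one entry for "Cardiac tamponade" and another for "Pericardial effusion or rub".

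For reporting, section 6.2.4 plans to present "All adverse events, and whether or not each is device-related or procedure-related". Sections 9.0 and 21.0 add quarterly safety reports to the FDA, and section 11.1 has the DSMB review safety data. Section 9.0 has the CEC adjudicate every adverse event from the forms, the medical records and its own expertise. Section 11.2 describes the CEC's task as deciding whether an event is related to the device or procedure.

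**The concern.** Tamponade is ordinarily understood as pericardial fluid that compromises the circulation. The written definition leaves out the compromise and so defines an effusion, confirmed or not. A site that sees a small effusion with no symptoms has two labels available and no rule for choosing between them. The same label could cover a suspected trace of fluid and a collapse that needs drainage.

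This matters for the safety description of the device. It is fixed to the right-ventricular endocardium by a helix (section 14.2.1), and fixation and the implant procedure are among the novel features on which the risk assessment focused (section 13.1). Section 13.4 says that the residual risks of novel features need clinical data before they can be estimated with confidence. Readers of the adverse event tables will want to know how many subjects had fluid and how many had compromise. The written definition does not let the tables answer that.

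**Working it through.** **Step 1: set the uses side by side.**

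| Place | Fluid or effusion | Tamponade |
|---|---|---|
| 6.2.5, tamponade definition | is the definition | confirmed or suspected fluid |
| 6.2.5, perforation definition | listed as one sign | listed as another sign |
| 6.2.5, SAE note | named, serious if it requires or prolongs hospitalization | not named |
| 9.0, Table 5 | own entry, with rub | own entry |

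**Step 2: substitute the definition where the term is used.** In "the accumulation of fluid in the pericardium, cardiac tamponade, or subject symptoms", replacing tamponade by its definition gives fluid, then confirmed or suspected fluid. The second item adds only the suspected cases. In Table 5, every event that fits the effusion entry also fits the tamponade entry. As written, effusion is a subset of tamponade, which reverses the ordinary relation.

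**Step 3: look for a repair elsewhere.** The text of section 6.2.5 is not blacked out at this point. No visible section adds a criterion that separates the two events. The plan does separate by severity or consequence for other events. Section 6.4.5.1 distinguishes an access-site hematoma that needs intervention from one that does not, and section 6.2.5 makes dislodgement depend on a change in threshold or sensing. The CEC could in practice separate the cases, but no section asks it to classify event type or gives it a criterion.

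**Step 4: check whether the label reaches the hypothesis tests.** A complication in section 6.2.5 depends on seriousness and on relation to the device or procedure, or on preventing the implant. None of these uses the word tamponade. With the exact two-sided 95% interval:

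- 6 months, n = 300, goal 86%: success needs at least 270 complication-free (lower bound 86.03%), so at most 300 − 270 = 30 failures.
- 12 months, n = 600, goal 84.5%: success needs at least 525 (lower bound 84.58%), so at most 600 − 525 = 75 failures.

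Moving an event between the tamponade and effusion labels changes neither its seriousness nor its relatedness, so the failure counts stay the same.

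**Step 5: size.** The documents give no tamponade or effusion rate, so there is no plan figure to reproduce. Let t be the rate of fluid with compromise, e the rate of fluid without it, and f the share of the latter coded as tamponade. Then

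reported / true = (t + f·e) / t.

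With f = 0 the ratio is 1. With f = 1, and purely as an assumption t from 0.5% to 1.5% and e from 0.25% to 2%:

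- smallest: (1.5 + 0.25) / 1.5 = 1.17
- largest: (0.5 + 2.0) / 0.5 = 5.0
- middle case, t = e = 1%, at the maximum enrolment of 667: 667 × 0.02 = 13.3 reported against 667 × 0.01 = 6.7 true, a ratio of 2.

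The ratio therefore lies between 1 and 5 across these assumed values. This shows how sensitive the count is to coding practice. It does not estimate what happened in the trial.

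**The case against.** The strongest reply is that clinicians know what tamponade is, have a separate effusion term in Table 5, and will use it sensibly. The adverse event form also records what intervention was needed and how the event ended (section 9.0), the SAE criteria separate a trace of fluid from a life-threatening event, and the CEC Charter or the form, neither of which is available here, may hold a working classification. Table 5 contains other overlapping terms, so separate entries alone do not prove separate categories. Much of this stands. It limits the harm, but it does not supply the missing criterion, and reliance on each site's own sense of the word is itself a source of inconsistency.

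Several stronger readings are tempting and should not be drawn:

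- A reader might infer that the trial cannot report a meaningful tamponade rate. Source records should allow cases to be sorted later; the plan simply contains no step to do so.
- A reader might infer that every effusion will be counted as tamponade. That is f = 1, the worst case. The scheduled tests include ECG and chest x-ray but no echocardiogram, so silent trace effusions would seldom be sought.
- A reader might take "New pericardial effusion more than trivial/mild, or requiring percutaneous/surgical drainage" in section 6.3.2 to mean that subjects can enter with tamponade as defined. That line sits under complications of a recent endovascular procedure and is not a general effusion criterion. Fluid present before implant is not an adverse event under section 6.2.5, which requires a link to the study device or intervention.
- A reader might infer distortion of the UADE test. That test requires a serious problem, both events are already listed as foreseeable, and Table 5 gives no incidence to distort.
- A claim about comparison with other pacing studies would need outside definitions that the documents do not give.

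**Conclusion.** The definition is wrong as written and is inconsistent with the way the same document uses the terms. Its effect is confined to the separate tamponade and effusion counts in the adverse event and safety reporting, which may be inflated or may mix different things by site. How far depends on coding practice and on event rates that the documents do not show, so the size is unknown. The conclusion assumes that sites or the CEC apply section 6.2.5 at least some of the time, and that no unseen charter or form overrides it. The primary and supplementary safety conclusions are not threatened. The correction is worth making because it is cheap and concerns an important cardiac event for this device.

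**What to change.** In section 6.2.5, define two separate events:

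- Pericardial effusion: fluid in the pericardial space that is not known to predate the implant procedure.
- Cardiac tamponade: pericardial fluid with haemodynamic compromise attributed to it.

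Have the CEC establish each from whatever evidence exists: imaging, drainage, surgery, autopsy or the clinical record. Imaging should not be a condition. No echocardiogram is scheduled, and an imaging requirement could drop an emergency or fatal case that was never imaged. Suspicion that the CEC does not accept should not count.

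Extend the CEC's role in section 11.2 to event type as well as relatedness. Report the two counts separately under section 6.2.4 and in the periodic safety reports. Implants have already taken place (section 14.1 refers to subjects still followed with an earlier pacemaker model), so re-label events already coded, using existing records.

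The cost is two definitions, one sentence on the CEC's role and a small amount of extra adjudication. No new tests or visits are needed, and no endpoint changes.
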